Feasibility of at Home Telehealth Yoga for Treating Chronic Pain

Study Protocol and Statistical Analysis Plan

NCT #: 04074109

November 22, 2021

Background

Chronic pain is a debilitating condition with high societal and economic costs. Pharmacological pain management includes opioids, which can be dangerous and ineffective after long-term use. Consequently, increased efforts are being made to find nonpharmacological treatment options for the management of chronic pain. For this reason, rigorous research on complementary and integrative health (CIH) for pain is a top priority and pain is the condition for which adults in the United States most often use complementary and integrative health. Chronic pain, and especially musculoskeletal pain is even more prevalent among veterans, and yoga has emerged as a popular and effective treatment option. The use of yoga to treat chronic pain has been endorsed by many organizations including the NIH, the American College of Physicians, and the VA. However, patients, especially rural and low-income patients, can encounter many barriers to practicing yoga, including travel costs and time, health conditions, bad weather, lack of transportation, and family responsibilities. One solution to overcome these barriers is to provide yoga at home using internet-based technology ("teleyoga"). Indeed, the provision of VA care via telehealth to increase access to those living far from VA medical facilities is a VA priority. Teleyoga is an innovative, potentially effective approach for treating chronic pain in veterans. Research evaluating the acceptability or efficacy of teleyoga is very limited. Our pilot data indicate that teleyoga is safe and has similar efficacy to in-person yoga for treating several common conditions in veterans, including chronic musculoskeletal pain (Schulz Heik et al., 2017). However, our teleyoga experience is limited to group yoga instruction via an audiovisual link to one or more outpatient clinics. This clinic-based modality requires participants to travel to a clinic for yoga instruction and does not overcome the multiple barriers associated with in-person care. Attempts by other groups to deliver at-home teleyoga have not overcome all the technical barriers encountered (Donesky et al., 2017). Standard Video conferencing software offers an exciting opportunity to develop at-home teleyoga using a well-resourced, scalable, and technologically advanced system. This study will focus on the treatment of chronic musculoskeletal pain, as it is the most common type of chronic pain in veterans and nonveterans (Kerns, 2018) and responds well to yoga.

Objectives

The primary objective is to test the feasibility of treating chronic pain with yoga delivered via telehealth. We will modify an existing yoga intervention for chronic musculoskeletal pain and address the technical challenges of at-home teleyoga. Then, using the modified intervention, we will demonstrate the feasibility of conducting a randomized controlled trial involving at-home teleyoga.

Specific Aims and Hypothesis

Specific Aims:

1. Modify an existing yoga intervention for chronic musculoskeletal pain and address the technical challenges of at-home teleyoga.
2. Demonstrate the feasibility of conducting a randomized controlled trial involving at-home teleyoga.

Hypothesis 1 (primary): a) Treatment satisfaction as measured by the Multi-Dimensional Treatment Satisfaction Measure will be neutral or positive for all factors. B) Treatment satisfaction will be at least neutral for all items.

Hypothesis 2 (secondary): a) It will be feasible to recruit 30 participants over a 3-month period and deliver yoga in-person or via at-home teleyoga while maintaining a retention rate commensurate with other similar studies. b) Fidelity of treatment delivery will be acceptable as measured by scoring of taped sessions. c) We expect participants will complete the PROMIS measures with a missing data rate not to exceed 15% per participant. d) The yoga intervention will be safe with no serious adverse events in either treatment group.

Study Design

This study aims to investigate the feasibility of at-home teleyoga for veterans with chronic musculoskeletal pain. We will demonstrate the feasibility of conducting a randomized controlled trial involving at-home teleyoga. We will randomize veterans (N=30) with chronic musculoskeletal pain to at-home teleyoga or in-person yoga. Primary feasibility outcomes will include recruitment rates, retention, protocol adherence, participant satisfaction from semi-structured questionnaires, adverse events, treatment fidelity, and rates of completion of study instruments. Feasibility will be determined by comparison to benchmarks from studies that used similar interventions and populations.

We intend to recruit local (residing in the San Francisco Bay Area), outpatient adult veterans with chronic musculoskeletal pain to enroll in this clinical trial. This research proposal will use randomization after baseline assessments to assign participants (n=30) to at-home teleyoga or in-person yoga (n=15 per group). Randomization will occur by identifying group membership in 30 sealed envelopes and having each participant draw one envelope. To be representative of the veteran population at VAPAHCS Health Care System (VAPAHCS) each group will have 1-2 females.

All human subjects research will be performed at VAPAHCS in Palo Alto, California or at the homes of the veterans (residing in the San Francisco Bay Area) who receive the at-home teleyoga group. There are no other collaborating sites where human subjects research will be performed.

Month					
1	2	3	4	5	6
Recruit (n=30)			Run in-person yoga groups (n=15) Run at-home teleyoga groups (n=15)		

Table 1. Recruitment Table

Group assignment and randomization

Eligible participants will be added to a cohort list; when 30 have been identified, the study team will schedule baseline assessments. After the baseline assessments, participants will be randomized to in-person or at-home teleyoga (n=15 per group). Randomization will occur by identifying group membership in 30 sealed envelopes and having each participant draw one envelope. Each group will contain 1-2 females, to be representative of the veteran population at VAPAHCS.

Statistical Plan and Data Analysis

Fidelity and Missing Data Benchmarks

Fidelity: The instructors will review the video recorded sessions using a manual checklist for instructor adherence to the yoga manuals, which will consist of a Yes/No for each procedure or instruction.

Missing Data: Like similar behavioral outcome measures, we expect missing data in the PROMIS-PI measures not to exceed 15%.

The main analytic strategy will be descriptive statistics at pre- and post-intervention assessments in each arm. We will then preliminarily compare the two conditions in line with the intention to treat principle. The purpose of these comparisons is not to provide formal inference but provide preliminary information to guide the adequately powered future trial.

The estimated changes and their group differences in pain and depression measured by the BPI-SF and BDI-II will provide preliminary data on target engagement and therefore inform and shape the future trial in terms of elucidating the mechanism of action. We will make a rigorous effort to minimize missing data. Nonetheless, we expect some attrition by post-intervention assessment. For group comparisons, we will focus on collecting preliminary data on clinical significance (i.e. effect size), instead of making formal inference (i.e., *p*-value).

Inclusion/Exclusion Criteria

Identify inclusion criteria.

- Veteran of the United States Armed Forces ≥ 18 years old
- Diagnosis of chronic musculoskeletal pain > 6 months (Dworkin, 2012)
- Minimum pain intensity at screening visit: pain rated ≥ 4 on a 0-10 Numeric Rating Scale (NRS) as recommended by IMMPACT guidelines. We intend to use the NRS from the Defense and Veterans Pain Rating Scale (DVPRS).
- Has not begun new pain treatments or medications in the past month.
- If on a psychotropic medication regimen: stable regimen for at least 4 weeks prior to entry to the study; willingness to remain on a stable regimen during the 12-week acute treatment phase.
- English literacy.
- Wireless internet connection at home.

Identify exclusion criteria.

- Participation in another concurrent clinical trial.
- Back surgery within the last 12 months.
- Back pain potentially attributed to a specific underlying cause, disease, or condition.
- Baseline pain < 4 or ≥ 9 on a 0-10 Numeric Rating Scale (NRS) as recommended by IMMPACT guidelines. We intend to use the NRS from the Defense and Veterans Pain Rating Scale (DVPRS). For ratings ≥ 9 , we will refer the veteran to the provider for prompt care.
- Unstable, serious coexisting medical illness.
- Unstable, serious coexisting mental illness or psychiatric conditions.
- practiced yoga ≥ 1 x in the past 12 months
- Active current suicidal intent or plan.

Criteria will be applied based on the informed consent process, a review of the participant's VA electronic medical record (EMR) and a screening interview.

The study will exclude participants with back pain potentially attributed to specific underlying causes, diseases, or conditions (e.g. pregnancy, previous back surgery, fractures, dislocations); unstable, serious coexisting medical illnesses (e.g. Congestive Heart Failure, cancer, COPD, dementia); unstable, serious coexisting mental illnesses or psychiatric conditions (e.g. unmanaged psychosis, active substance abuse); or minimal or maximal pain ratings at the time of screening (<4 or \geq 9 on a 0-10 Numeric Rating Scale (NRS) as recommended by IMMPACT guidelines). We intend to use the NRS from the Defense and Veterans Pain Rating Scale (DVPRS).

Participants on a psychotropic medication regimen will be asked to maintain a stable regimen for at least four weeks prior to entry to the study and remain on a stable regimen during the 12-week acute treatment phase, under the patient's medical care team. Excluded participants will be reconsidered for eligibility after stability on medication is achieved. Involvement in medical treatments will be tracked closely through self-report and clinician interviews, and we will use this information when analyzing the results. Participants with active current suicidal intent or plan will be excluded. Participants at risk for suicide will be required to establish a written safety plan involving their primary psychiatrist and the treatment team, prior to entering the clinical trial.

All participants will be able to read, verbalize understanding, and voluntarily sign the Informed Consent and Health Insurance Portability & Accountability Act (HIPAA) prior to the performance of any study-specific procedures or assessments.

Since we seek to assess the feasibility of providing at-home teleyoga via VA Video Connect, all participants will need access to wireless internet connection at home.

Informed Consent Process

Veterans will be recruited from three sources: the VAPAHCS Pain Clinic, local advertising, and web-based advertising. These sources will result in either 1) the potential participant calling the study team or 2) with the participant's consent, the study staff contacting them directly. Study candidates will be invited to the VAPAHCS for a screening visit, during which the Project Manager will obtain informed consent and review the Health Insurance Portability & Accountability Act (HIPAA) document.

The informed consent process, including the HIPAA document, is estimated to take about 30-60 minutes. It will take place in a quiet office or interview room, or via video link.

1. The Project Manager will explain the information contained in the written informed consent (purpose, procedures, risks, benefits, alternatives to participation, etc.) and HIPAA documents to the study candidate verbally, in lay language.

- a. The Project Manager will check for comprehension, allow the study candidate ample opportunity to ask questions throughout the process, and repeat the information, as necessary.
 - b. Care will be taken to inform the study candidate that his/her participation is entirely voluntary, and they may withdraw at any time and for any reason without penalty or loss of benefits to which they would otherwise be entitled.
 - c. Study candidates will then be asked to carefully read the informed consent form to consider whether or not to participate in the research and to ask questions.
 - d. To ensure that the study candidate understands the research, they will next be asked to summarize the consent form and HIPAA addendum, with a special focus on the discomforts, risks, benefits, and confidentiality sections.
2. If the study candidate demonstrates (by stating in his/her own words) an understanding of the purpose, risks, and benefits of the study and agrees to participate in the study, he/she will be asked to initial each page, in addition to sign and date the last page of the consent form and the HIPAA document.
 3. The Project Manager who oriented and obtained informed consent will sign and date the informed consent form.
 4. The Project Manager will provide the enrolled participant with a photocopy of the original signed copy and keep the original signed copy in a binder in a locked cabinet.

The emphasis on the voluntary nature of participation is designed to minimize the possibility of coercion or undue influence on participation. The study candidate will be given time to understand the written informed consent form and make an informed decision. All treatments for this study will be provided in group formats, so potential participants will be reminded that full anonymity cannot be maintained.

Following the informed consent process, the enrolled participant will complete other measures.

Screening Procedures

Potential participants (n=30) will be invited to the VAPAHCS for a screening visit. The Project Manager will obtain informed consent and review the Health Insurance Portability & Accountability Act (HIPAA) document. After obtaining informed consent, a trained researcher will collect demographic information (Demographic Questionnaire). Screening for protocol eligibility will include the Clinical Questionnaire and DVPRS.

Study Assessments

Demographics Questionnaire: Documents age, gender, education, and race/ethnicity.

Clinical Questionnaire: Self-report document focusing on the existence of 78 health symptoms taken from a list of ICD-9 codes that are highly likely to represent chronic pain.

Medication Use: Self-report of all current pharmacological and non-pharmacological treatments.

Yoga Home Practice Log: Log for participant to document their yoga home practice on non-treatment days.

BDI-II Beck Depression Inventory-II (BDI-II): Contains 21 self-report questions, scored on a 0-3 scale, related over the past two weeks to sleep, appetite, punishment, suicide, and interest in sex.

Brief Pain Inventory-Short Form (BPI-SF): Assesses intensity and impact of pain on functioning on a 0-10 rating scale. Interference is assessed on daily life (general, walking, work, mood, enjoyment, relationships, sleep). The BPI is recommended by the Initiative on Methods, Measurement, and Pain Assessment in Clinical Trials (IMMPACT) group for inclusion in clinical trials evaluating pain.

Defense and Veterans Pain Rating Scale (DVPRS): A five-item scale: one 0-10 pain intensity numeric rating scale and four supplemental items measuring functional outcomes (general activity, sleep, mood, level of stress). The pain intensity scale is designed to improve upon existing scales by using visual cues and word descriptors to anchor pain ratings with perceptual experiences and limitations imposed by pain.

PEG: A 3-item pain measure derived from the Brief Pain Inventory and validated in ambulatory care settings. It includes 1 severity item (average pain) and 2 interference items (enjoyment of life and general activity).

Patient-Reported Outcomes Measurement Information System-Pain Interference

(PROMIS-PI) (108): Examines the extent to which pain hinders engagement over the past seven days with social, cognitive, emotional, physical, recreational activities, and physical functioning through Likert-type 1-5 scales.

Treatment Satisfaction: Assessed using the Multi-Dimensional Treatment Satisfaction Measure (MDTSM). The measure consists of 11 subscales assessing treatment process and outcome attributes. Each subscale has 1-8 items (see Table 5). Each question except the Discomfort subscale is rated on a five-point scale ranging from “not at all (0)” to “very much (4)”. Thus, a score of 2 represents a rating of neutral satisfaction. The instrument was developed for behavioral interventions and is designed to provide a comprehensive set of treatment attributes to consider when evaluating treatments in the context of pilot studies. It is designed to be completed after exposure to an intervention, to point to aspects of treatments that are viewed favorably or unfavorably. The MDTSM is relevant to many types of behavioral interventions and can be tailored to our yoga intervention. The MDTSM subscales demonstrates good internal consistency, reliability, and validity.

	Data Collection			
	Screening	Baseline	Yoga (wks 1-12)	Post-treatment
Background				
Consent Form	×			
Demographic Questionnaire	×			
Clinical Questionnaire	×			
Yoga Medical Clearance Form	×			
Medical Use		×		×
Yoga Home Practice Log			×	
Mental Health				
BDI-II		×		×
Pain/QOL/Physical				
BPI-SF		×		×
DVPRS	×			
PEG	×	×		×
PROMIS-PI		×		×
Behavioral				

Treatment Satisfaction				x
Provider Suggestions				x
Patient Safety			x	x
Treatment Fidelity			x	

Table 2. Study Measures and Timetable of Data Collection

Yoga Treatment

Participants will be randomized to in-person yoga (n=15) or online yoga (n=15). Yoga classes will be 75-minutes and will be delivered by a yoga instructor once a week over a course of 12 weeks in-person or online.

Yoga (in-person): Veterans in the in-person yoga group will attend yoga classes at VAPAHCS. The yoga instructor will provide weekly instruction at the VAPAHCS in a telehealth-equipped conference room.

Yoga (online): The yoga instructor will provide weekly instruction using approved teleconferencing software either from an offsite location or from the VAPAHCS in a telehealth-equipped conference room.

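### Does the 15% limit on missing PROMIS data need a new definition because Hypothesis 2c states it per participant and the statistical plan gives no unit?

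*Combined protocol and SAP*

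**What the plan says.** The 15% figure appears twice in the combined protocol and SAP.

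- Specific Aims and Hypothesis, Hypothesis 2c (labelled secondary): "We expect participants will complete the PROMIS measures with a missing data rate not to exceed 15% per participant".
- Statistical Plan and Data Analysis, under the heading "Fidelity and Missing Data Benchmarks": "we expect missing data in the PROMIS-PI measures not to exceed 15" percent, with no unit or denominator.

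Five other places bear on how it is read.

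- Table 2 schedules PROMIS-PI at baseline and post-treatment only.
- Group assignment and randomization: "After the baseline assessments, participants will be randomized to in-person or at-home teleyoga (n=15 per group"). A participant who drops out after randomisation should therefore already have a baseline form.
- Statistical Plan and Data Analysis, in the later paragraph on the BPI-SF, the BDI-II and group comparisons: "We will make a rigorous effort to minimize missing data. Nonetheless, we expect some attrition by post-intervention assessment". No rate is given.
- Hypothesis 2a deals with dropout on its own terms: recruitment and delivery are to succeed "while maintaining a retention rate commensurate with other similar studies".
- Study Design lists retention and "rates of completion of study instruments" as separate items among the primary feasibility outcomes, and adds: "Feasibility will be determined by comparison to benchmarks from studies that used similar interventions and populations".

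**The concern.** In a feasibility trial without formal inference, benchmarks are the nearest thing to decision rules, so an ambiguous one deserves a look. One statement of the 15% carries a unit and the other does not. Neither says whether a form that was never returned counts as missing.

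With two forms per person the choice can matter. If missing forms count and every participant must meet the limit, the first dropout breaches it. If the same 15% applies to post-treatment forms, or to all forms pooled, several dropouts are allowed. The plan expects some attrition and mentions it directly after the effort to limit missing data, which suggests that dropout might count. At stake would be the pass or fail verdict on Hypothesis 2c, with a denominator that could be picked once the data are in hand.

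**Working it through.** **Inputs.** 30 participants randomised, 15 per group (Group assignment and randomization). Two PROMIS-PI forms each (Table 2), so 30 × 2 = 60 forms. Limit 15%, with exactly 15.0% allowed because the wording is that the rate should not exceed it. The 15% is stated as an expectation and not derived from anything, so there is no calculation in the plan to reproduce.

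**Step 1: form-level readings.** Let d be the number of randomised participants with a baseline form and no post-treatment form, with nothing else missing.

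| Reading | Rate | Passes for | Check at the boundary |
|---|---|---|---|
| Each participant at or below 15% | 1/2 = 50% for every dropout | d = 0 | 50% > 15% at d = 1 |
| Post-treatment forms only | d/30 | d ≤ 4 | 4/30 = 13.3%; 5/30 = 16.7% |
| All forms pooled | d/60 | d ≤ 9 | 9/60 = 15.0%; 10/60 = 16.7% |
| Mean of participants' rates | (0.5 × d)/30 = d/60 | d ≤ 9 | same as pooled |

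Under these readings at least two verdicts differ for every d from 1 to 9.

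**Step 2: how often that would happen.** The documents give no attrition rate, so the rates below are assumptions. With independent dropout at rate q, d is binomial (30, q), and the chance of passing is P(d ≤ k) with k = 0, 4 or 9. For example, P(d = 0) at q = 5% is 0.95^30 = 0.215.

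| Assumed q | k = 0 | k = 4 | k = 9 |
|---|---|---|---|
| 5% | 21% | 98% | over 99.9% |
| 10% | 4.2% | 82% | over 99.9% |
| 15% | 0.8% | 52% | 99% |
| 20% | 0.1% | 26% | 94% |

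**Step 3: what the spread depends on.** The 1-to-9 range needs four conditions:

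1. A wholly missing form counts as missing data.
2. Per participant means that every participant must pass, and not an average.
3. Baseline forms are complete.
4. Exactly 15.0% passes.

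If condition 2 is replaced by an average, Hypothesis 2c gives d/60, the same as the pooled reading of the statistical plan at every d. If condition 1 fails, d does not enter the benchmark and both tables fall away.

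**Step 4: is condition 1 the natural reading?** Over two forms one person's missing rate is 0%, 50% or 100%. A limit of 15% would then act exactly like a limit of 0%, which is an odd way to write a rule. Counted over items, 15% does real work. The documents do not give the number of PROMIS-PI items. If it were 8 (an assumption), two forms hold 16 responses, 0.15 × 16 = 2.4, and a participant could skip 2. At an assumed 40 items, 0.15 × 80 = 12.

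The item reading also fits the rest of the plan. Hypothesis 2c speaks of participants completing the measures, and Hypothesis 2a already takes dropout. The statement that some attrition is expected also tells against a benchmark that fails at the first dropout.

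**The case for a change.** The strongest case for acting is that this is a feasibility study and its benchmarks carry the conclusion. The 15% sits under a heading that calls it a benchmark, instrument completion is listed among the primary feasibility outcomes, and feasibility is to be judged against benchmarks. Neither statement limits the 15% to skipped items. Even if per participant means an average, the pooled and post-treatment counts still part ways at 5 to 9 dropouts. A single clause would settle the matter at almost no cost.

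Part of this stands. The numerator and denominator are undefined, and a clarifying clause would do no harm. The rest does not carry. Both statements word the 15% as an expectation, and no decision rule is tied to it. Study Design says feasibility benchmarks come from similar studies, and the 15% is one indicator among several.

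The worry about choosing a denominator afterwards is also weak, because every form-level rate above is a function of the single count d. Once d is reported by arm, any reader can apply any denominator.

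The obvious repair would itself be open to dispute. A cap of 4 of 30 without a post-treatment form amounts to a retention floor of 26/30 = 86.7%. Hypothesis 2a instead ties retention to comparable studies, and nothing in the documents favours that cap over the pooled count or the item reading.

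**Conclusion.** No change to the plan is needed. The two statements are compatible: the one in the statistical plan can be read as shorthand for Hypothesis 2c. The tolerances of 0, 4 and 9 dropouts of 30 are right as arithmetic, but they apply only if wholly missing forms count towards the 15%, and the first of them also needs every participant to pass. On the more natural reading, skipped items on returned forms, dropout does not enter and is judged as retention under Hypothesis 2a.

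The gap left is an unstated unit for a descriptive expectation. The statistical plan disclaims formal inference and reports by arm before and after treatment. An analyst would sensibly give item-level missingness within returned forms, give the number of missing forms by arm, and show dropout with the retention result. The effect is confined to how one secondary expectation is summarised.

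This conclusion rests on the absence of any stated go/no-go rule for the 15% and on reading Hypotheses 2a and 2c as separate outcomes. The pass probabilities rest on assumed attrition rates and independence, and should not be read as forecasts.

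### Hypothesis 2d equates safety with zero serious adverse events: one unrelated event would contradict it, and zero events in 15 per arm would not show safety

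*Combined protocol and SAP*

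**What the plan says.** Under Specific Aims and Hypothesis, part (d) of the secondary hypothesis reads "The yoga intervention will be safe with no serious adverse events in either treatment group". It has no relatedness qualifier and no confidence limit.

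Study Design gives safety a further role: "Primary feasibility outcomes will include recruitment rates, retention, protocol adherence, participant satisfaction from semi-structured questionnaires, adverse events" are all named there. It adds "Feasibility will be determined by comparison to benchmarks from studies that used similar interventions and populations". No safety benchmark follows. The subsection Fidelity and Missing Data Benchmarks covers only instructor fidelity and missing PROMIS-PI data. Table 2 schedules a Patient Safety item during weeks 1-12 and after treatment but does not say what is recorded. The document gives no SAE definition, no attribution procedure, no background SAE rate and no planned interval for event rates.

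The plan is to "assign participants (n=30) to at-home teleyoga or in-person yoga (n=15 per group"). Classes are "delivered by a yoga instructor once a week over a course of 12 weeks in-person or online". On completeness of follow-up it says "Nonetheless, we expect some attrition by post-intervention assessment", without a rate.

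**The concern.** Hypothesis 2d can mislead in two directions.

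First, it can fail for a reason that has nothing to do with yoga. The medical exclusion is worded "Unstable, serious coexisting medical illness", so veterans with stable chronic illness may enrol, and there is no upper age limit. An unrelated hospital admission within 12 weeks is plausible. Read literally, one such event in either arm contradicts the hypothesis.

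Second, it can be met without safety having been shown. Zero events in a small group is compatible with a rate that most readers would not call safe.

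At stake is what the report may say about at-home delivery, which is the new element here: the Background says that the team's earlier teleyoga experience was limited to instruction linked to clinics. An unqualified statement of safety would overstate the evidence passed to the future trial. A failed hypothesis caused by one unrelated admission would mislead in the other direction.

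**Working it through.** The plan gives no SAE rate, safety margin or sample-size derivation, so there is no figure of its own to reproduce. The inputs from the document are n = 15 per arm and N = 30 overall (Study Design). The event rates p below are assumptions, shown over a range. Participants are treated as independent.

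**1. Chance that at least one SAE occurs among 30, whatever its cause:** 1 − (1 − p)^30.

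| Assumed 12-week SAE rate per person | Chance of at least one in 30 |
|---|---|
| 0.5% | 1 − 0.995^30 = 14% |
| 1% | 1 − 0.99^30 = 26% |
| 2% | 1 − 0.98^30 = 45% |
| 5% | 1 − 0.95^30 = 79% |

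**2. What zero events would exclude.** The exact (Clopper-Pearson) two-sided 95% upper limit for 0/n is 1 − 0.025^(1/n). The one-sided 95% limit is 1 − 0.05^(1/n).

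| Observed | Two-sided upper limit | One-sided upper limit |
|---|---|---|
| 0/15 (one arm) | 21.8% | 18.1% |
| 0/30 (both arms) | 11.6% | 9.5% |
| 0/12 (illustration of attrition) | 26.5% | 22.1% |

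The number needed for zero events to exclude a rate u with one-sided 95% confidence is ln(0.05)/ln(1 − u), rounded up. This gives 29 for 10%, 59 for 5%, 149 for 2% and 299 for 1%.

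**3. Chance of meeting the hypothesis when a real risk exists.** Zero events are required in both arms, and both arms receive yoga. If both carry the same true SAE rate p, the chance of meeting it is (1 − p)^30:

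- p = 5%: 0.95^30 = 21%
- p = 10%: 0.90^30 = 4%

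A single arm of 15 shows no events with probability (1 − p)^15:

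- p = 5%: 0.95^15 = 46%
- p = 10%: 0.90^15 = 21%

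The single-arm figures matter for a claim about teleyoga alone. They are the chance of meeting the whole hypothesis only if the other arm has no risk.

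**The case against.** The strongest reply is that 2d is an expectation, not a decision rule. It belongs to a secondary hypothesis, and no stopping or progression decision depends on it. The analysis is descriptive, group comparisons disclaim formal inference, and no 30-person pilot can establish safety. All of this stands and limits the weight of the point. It does not remove it: the disclaimer concerns comparisons between groups, whereas 2d makes a separate claim about the intervention itself.

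Four stronger readings are tempting, and the document does not support them.

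- *That the plan states an all-cause rule.* It does not. The sentence is unqualified, and because its subject is the yoga intervention, a reading limited to related events is also natural. The defect is that nothing settles the question.
- *That background events would mainly drive the result.* No rate is given. At an assumed 0.5%, the hypothesis would be met 86% of the time; at 1%, 74%.
- *That unstable serious illness is the only barrier to entry.* Inclusion/Exclusion Criteria also exclude recent back surgery, back pain with a specific cause, pain ratings of 9 or more, and active suicidal intent or plan. A written safety plan is required for those at risk of suicide, and Table 2 lists a yoga medical clearance form at screening. These may lower the background rate, but stable illness remains eligible.
- *That the hypothesis would be met 46% or 21% of the time at true rates of 5% or 10%.* Those figures describe one arm. With the same risk in both arms, the figures are 21% and 4%.

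**Conclusion.** The point holds as a modest correction. Hypothesis 2d ties safety to a zero count without saying which events count or how uncertain that count is.

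The second half of the point is firm, because it needs only the stated sample sizes: zero events would leave SAE rates of up to 21.8% per arm and 11.6% overall within the exact two-sided 95% interval. The first half is conditional. Over assumed rates of 0.5% to 5%, the chance that at least one SAE contradicts the sentence as worded runs from 14% to 79%, and the document does not say where in that range this population lies.

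A reader might infer that the trial's feasibility verdict turns on this sentence. The document does not support that: feasibility is to be judged against benchmarks from similar studies, and 2d has no formal consequence. What changes is what the trial may fairly report about safety.

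**What to change.** Replace the claim of safety in 2d with an estimate, and add to Statistical Plan and Data Analysis:

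- Report all-cause SAEs, SAEs judged related to yoga sessions or home practice, and adverse events, by arm and overall, as n/N with exact (Clopper-Pearson) 95% intervals.
- If no SAE occurs, write that no SAEs were observed and give the upper limit (about 22% per arm and 12% overall at full enrolment, wider if fewer are followed). Do not write that the intervention is safe.
- If 2d keeps a zero-event expectation, apply it to related SAEs and always show the all-cause counts beside it. Adding the relatedness qualifier alone would not be enough, because it keeps the zero threshold and makes it easier to meet.

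The cost is small: a few sentences, an SAE definition and an attribution step, neither of which the document now contains. No extra participants or visits are needed. There are two downsides. The safety statement becomes less favourable. Relatedness would be judged by staff who know the arm, which the all-cause counts offset.
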